2-33 (ed 3.1) -- meeting limits and guidelines for peripheral nerve stimulation, patient thermal, SAR limit, acoustic noise, flammability rating UL94-5VA for safety covers, hydrostatic pressure, electrical hazards, dielectric strength and pinch point. The MRI scans in this study will also utilize operational parameters within FDA guidelines for Nonsignificant Risk thus an Investigational Device Exemption (IDE) from FDA should not be necessary.

- Saliva sample as described in DETAILS OF RECRUITMENT, DESIGN AND TREATMENT below)

4. Treatment Phase: iTBS-TMS . Active iTBS-TMS Treatment Group – will receive a total of 20 treatments delivered 5-6 days/week, two (2) to

(3)treatments per day, over 2 consecutive weeks. Sham Treatment group will receive the same frequency and duration of treatment, without actual administration of iTBS-TMS. The majority of participants will be recruited from Palo Alto VA residential treatment programs; therefore, 24 hour monitoring for any adverse events will be in place as an additional layer of participant safety.

5. Post-Treatment Phase: Within 3-4 days of completion of the Treatment Phase, all participants will repeat neurocognitive assessment, select psychiatric assessment measures, select alcohol and substance questionnaires, 3 Tesla Magnetic Resonance Neuroimaging and blood draw. During this time, all participants will be receiving treatment-as-usual at the VA clinics, and scheduling of iTBS-TMS will be arranged as not to interfere with their daily treatment curriculum.

6. Monthly Follow-ups: For 1 year following completion of

Title : Transcranial Magnetic Stimulation for the Treatment of Veterans With Alcohol Use Disorders
Approval Period: 02/28/2025 - 02/28/2026

active/sham iTBS-TMS treatment, participants will be contacted monthly, via telephone or in person, to complete brief standardized measures of alcohol and substance use, as well as craving to assess for changes in these variables over the preceding 30 days. These brief contacts will be 15-20 min in duration and tracking sobriety is the primary outcome measure of this study.

DETAILS OF RECRUITMENT, DESIGN AND TREATMENT

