Design, Treatment Phase and Treatment Arms: This is a double-blind randomized group design, which will enroll 100 participants. After screening and baseline procedures, participants will be randomized to active or sham rTMS conditions (50 active, 50 sham); thus participants will have a 50% probability of receiving active treatment. Participants will receive 20 iTBS-TMS sessions over the course of 2 weeks. Participants will be required to be abstinent from alcohol and illicit substances for 5 days and demonstrate no clinically significant withdrawal symptoms prior to the first iTBS-TMS session.

Rationale for Brain Region Site: The left dorsolateral prefrontal cortex (DLPFC) was chosen as the rTMS stimulation site given excitatory transcranial magnetic stimulation to this region has been demonstrated to decrease cravings in non-Veterans with AUD. Additional stimulation of this site has been robustly shown to be associated with decreased unipolar depressive symptomatology; depressive disorders are highly comorbid in Veterans with AUD.

Duration of Treatment Phase: Active iTBS-TMS Treatment Group – will receive a total of 20 treatments delivered 5-6 days/week. Participants will typically receive two treatments per day (Monday-Friday), over 2 consecutive weeks; inter-treatment interval will be at least 2 hours. However, in the event the participant is unable to complete the typical two iTBS-TMS sessions per day due to participant or research personnel illness, scheduling issues, or other unforeseen circumstances. There have been no adverse events reported in the literature implementing multiple iTBS sessions per day in any population. Sham Treatment group will receive the same frequency and duration of treatment, without actual administration of iTBS-TMS. For both the active and sham iTBS-TMS groups, sessions will typically be conducted prior to the beginning of the participants treatment day, and at lunch, as to not interfere with their treatment-as-usual in the VA substance treatment clinics.

Procedures for Delivery of rTMS Sessions:

1. Anatomical localization of the left DLPFC for the stimulation coil will be individualized for each participant and achieved through standardized procedures for EEG electrode placement, optimized for transcranial magnetic stimulation.

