2. Motor Threshold MT Elicitation: Inherent to the safe and accurate dosing of iTBS-TMS stimulation, resting MT elicitation will be performed according to established protocols, which have been in use since 1994. This protocol is well-established as an effective method for MT Elicitation, widely implemented within both sham-controlled

Title : Transcranial Magnetic Stimulation for the Treatment of Veterans With Alcohol Use Disorders
Approval Period: 02/28/2025 - 02/28/2026

transcranial magnetic stimulation research with demonstrated safety. MT will be calculated for all participants prior to randomization.

3. iTBS-TMS Dosing: Dosing of iTBS-TMS will be delivered at 120% of the participants active MT adjusted to the skull to cortex distance (via each participants structural MRI), as this is documented to modulate the desired cortical target, and is not associated with any adverse events. Six hundred (1200) pulses of iTBS-TMS at 50 Hz will be utilized, consistent with standard parameters. There will be 10 trains of 3 pulses at 50Hz every 200ms (50Hz over 5Hz), which is 30 pulses per theta burst train. Twenty (40) trains will be delivered to achieve 1200 pulses over approximately 6 minutes.

4. Sham Control and Blinding Methods: The sham-control and blinding methods will be the same as used in TMS trials in which investigator and participant blinding to group assignment was carefully documented and achieved in previous clinical trials conducted with Veterans at VA medical centers. These methods involve:

(a) the Cool-B65-Active/Placebo Coil, which functions as both an active and sham coil; (b) scalp electrodes; and (c) a white-noise generator. The scalp electrodes are used to pass a low-voltage, low-electric current (2–20mA at no more than 100V) to mimic the sensation of receiving actual iTBS. The white-noise generator is used to send low-volume white noise to the subject's ears when magnetic stimulation pulses are initiated to hide the click noise the iTBS-TMS produces.

Post-Treatment Phase: Within 3-4 days of completion of the Treatment Phase, all participants will repeat neurocognitive assessment, select psychiatric assessment measures, select alcohol and substance questionnaires, random urine substance screen and alcohol breathalyzer, 3 Tesla Magnetic Resonance Neuroimaging and saliva samples as described above in Baseline/Pretreatment Assessment.

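### Pulses and trains per session each carry two values that differ two-fold (600 or 1200; 20 or 40), and the sentence on missed sessions is unfinished

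*Combined protocol and SAP*

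**What the plan says.** The dose per session is set out in Section 2a, Procedures for Delivery of rTMS Sessions, item 3 (iTBS-TMS Dosing). Three statements matter:

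- Pulses: "Six hundred (1200) pulses of iTBS-TMS at 50 Hz will be utilized".
- Structure of a train: "There will be 10 trains of 3 pulses at 50Hz every 200ms (50Hz over 5Hz), which is 30 pulses per theta burst train".
- Trains, total and duration: "Twenty (40) trains will be delivered to achieve 1200 pulses over approximately 6 minutes".

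The schedule is described in two places in Section 2a. Item 4 of the Protocol Summary says the active group "will receive a total of 20 treatments delivered 5-6 days/week, two (2) to" and continues "3)treatments per day, over 2 consecutive weeks". Duration of Treatment Phase says "Participants will typically receive two treatments per day (Monday-Friday), over 2 consecutive weeks; inter-treatment interval will be at least 2 hours". Both places give 20 sessions over two weeks, and both have sham match active in frequency and duration.

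The next sentence under Duration of Treatment Phase introduces an exception, "in the event the participant is unable to complete the typical two iTBS-TMS sessions per day due to participant or research personnel illness", adds scheduling problems and other unforeseen causes, and then ends. The text that follows is about adverse events in the literature. What is done when a day's sessions are missed is never stated.

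**The concern.** In item 3 the word and the numeral disagree for both quantities that define the session dose. This is not a slip in one digit. The two words agree with each other and so do the two numerals, so the paragraph holds two complete specifications of the active treatment. From this text alone an operator, a monitor or a later reader cannot say without inference how much stimulation a session contains.

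For the analysis, the stake is the definition of the intervention. Under Data Analyses, Primary Hypotheses 1a (logistic regression) and 1b (Cox regression) both enter treatment as one predictor, active against control, with no term for dose. That is adequate if all of the planned 50 active participants were treated to one specification. If they were not, the estimated effect would belong to no single defined treatment. The unfinished sentence is a smaller gap of the same kind: it leaves open how departures from the usual daily schedule are handled, which bears on adherence and on keeping the arms matched.

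**Working it through.** No sample size, power or error rate is involved. The check is direct arithmetic on the figures in Section 2a.

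**1. Pulses per train.** Ten bursts of three pulses: 10 × 3 = 30, which reproduces the stated 30. Item 3 uses the word train both for the three-pulse burst and for the 30-pulse unit. I take the 20 or 40 to count the 30-pulse unit, because counting bursts would give 20 × 3 = 60 or 40 × 3 = 120, and neither figure appears.

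**2. Pulses per session = trains × 30.**

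| Reading | Trains | Pulses per session | Over 20 sessions |
|---|---|---|---|
| Words | 20 | 20 × 30 = 600 | 20 × 600 = 12,000 |
| Numerals | 40 | 40 × 30 = 1200 | 20 × 1200 = 24,000 |

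Each row reproduces its own stated total exactly. The ratio is 2.0 per session and over the course.

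**3. The further mention of 1200.** The sentence on trains also gives the total to be achieved as 1200, with no word beside it. Twenty trains give 600 and do not reach that total; forty do.

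**4. Does the duration decide?** One train lasts 10 × 0.2 s = 2 s, and six minutes is 360 s.

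- 20 trains: 360 / 20 = 18 s per cycle, so a gap of 18 − 2 = 16 s.
- 40 trains: 360 / 40 = 9 s per cycle, so a gap of 9 − 2 = 7 s.

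No interval between trains is stated, so either gap is possible on the text and the duration alone does not separate the readings.

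**5. Does the schedule conflict?** Two sessions a day on ten weekdays gives 2 × 10 = 20, matching the total in both places. Section 8(m) gives 40 minutes a day over two weeks: 40 × 10 = 400 minutes, or 6.7 hours, close to the stated 6.5. A usual two per day lies inside a range of two to three. With the total fixed at 20, the range affects daily amount and spacing, not the number of sessions. The two-fold uncertainty in course dose therefore comes only from item 3.

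**The case against.** The strongest reply is that the text largely explains itself. One total stands without a competing word and only one train count reaches it, so the words look like remnants of an edit. Section 2a is also meant as a summary, and attachments not available here, including the grant application and a TMS session safety form, may hold a clean set of session parameters. Much of this stands: the two readings are not equally supported by the paragraph. It does not remove the need to correct it, because the current text carries both values and is the only dosing specification in the documents.

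Three stronger readings are tempting, and the documents do not support them.

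- **That the active arm contains two doses.** The documents give no history of when this paragraph changed and no record of delivered pulses. An edit before the first enrolment fits equally well.
- **That the two schedule statements contradict each other.** They do not, as step 5 shows. The real gap there is the unfinished sentence.
- **That daily exposure is uncertain three-fold, from 2 × 600 = 1,200 to 3 × 1200 = 3,600 pulses.** This multiplies the item 3 discrepancy by scheduling latitude that the plan openly allows. Three sessions every day would finish the course in 20 / 3 = 6.7 days, well short of two weeks, so the upper figure describes an exceptional day. At any fixed number of sessions per day the inconsistency is two-fold. The documents give no daily pulse limit against which to judge a safety consequence.

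**Conclusion.** The inconsistency is real and should be corrected. Item 3 specifies both 600 and 1200 pulses, and both 20 and 40 trains, per session: a factor of two, or 12,000 against 24,000 pulses over the course. This rests on the stated 30 pulses per train and 20 sessions, neither of which is in dispute. The pattern suggests an incomplete edit. Which figures are right is for the clinical team, and no view is taken here. The unfinished sentence on missed sessions is a separate and smaller gap that leaves the 20-session total unchanged.

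A mixed-dose active arm remains a possibility to be excluded by checking records; it is not a finding. Planned recruitment ended in 2023 (Resources, item d; Section 8m), so the main value now lies in verifying and accurately reporting what was delivered.

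**What to change.** 1. The clinical team reconciles item 3 into one set of figures, with words and numerals in agreement: trains per session, pulses per train, interval between trains, total pulses and duration. The word train should have one meaning throughout.
2. The clinical team completes the sentence on missed sessions under Duration of Treatment Phase so that it is consistent with item 4 of the Protocol Summary.
3. The study team confirms from device or session logs what was delivered, and the trial report states it.
4. Only if the logs show two doses: report the number of active participants at each, and add a sensitivity analysis of the primary outcome limited to active **and** sham participants randomised in the period when the final dose setting was in force. Restricting the active arm alone would not do. Sham participants receive no active stimulation and so have no dose to select on, and comparing part of the active arm with all sham participants would break the randomised comparison.

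The cost is a wording amendment and a log check. If step 4 is needed, the restricted analysis uses fewer than the planned 50 per arm and will be less precise, so it should be read as support for the full randomised comparison and not as its replacement.

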Monthly Follow-ups: For 1 year following completion of the treatment phase, participants will be contacted monthly, via telephone or in person, to complete a brief standardized measures of alcohol and substance use, as well as craving to assess for changes in these variables over the preceding 30 days. These brief contacts will be 15-20 min and tracking sobriety is the primary outcome measure of this study.

b) Explain how the above research procedures are the least risky that can be performed consistent with sound research design.

All procedures will be performed by staff trained specifically for the tasks for which

Title : Transcranial Magnetic Stimulation for the Treatment of Veterans With Alcohol Use Disorders
Approval Period: 02/28/2025 - 02/28/2026

they are responsible. All procedures, including the iTBS-TMS, and are considered low-risk procedures. iTBS-TMS is regarded as safe and without lasting side effects when established guidelines are followed. The primary serious adverse event associated with transcranial magnetic stimulation procedures are seizures, however, the estimated prevalence is very low at < 1%. In the case of transcranial magnetic stimulation-seizures, all have occurred during stimulation, there was no recurrence of seizures, and no incidences of status epilepticus. There have been no significant adverse cognitive, brain structural, neurologic or cardiovascular sequelae reported as a result of rTMS. Seizure risk will be minimized by careful patient selection by rigorously screening and exclusion of participants with history of seizure disorders or other conditions and medication use that increases risks of seizure. A seizure protocol is in place to avoid participant injury in the unlikely event that a seizure does occur attached. Overall, the risks to participants in this proposal are reasonable in relation to anticipated benefits, if any, to the participants, and the importance of the knowledge that may be expected to result.

c) **State if deception will be used. If so, provide the rationale and describe debriefing procedures. Since you will not be fully informing the participant in your consent process and form, complete an alteration of consent (in section 13). Submit a debriefing script (in section 16).**

N/A

d) **State if photo, audio or video recording will occur. Describe what will become of the photos or recording after use, e.g., shown at scientific meetings, erased. Describe the final disposition of the recordings.**

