Participants will not be compensated for study screening. Participants will receive a maximum of \$240 for all baseline and treatment phase and week 5 follow-up study procedures. If participants do not complete all baseline or post-treatment visit procedures, they will receive a pro-rated amount that is lower than \$200, based on how many procedures you completed. Participants will receive an additional \$50 if all monthly contact from week 9 – 25 are completed. Total possible compensation over 1 year is approximately \$290. The mechanism of payment will adhere to the VA mandated procedure: payment form, which the participant can obtain cash or check at the VA Palo Alto upon completion of Baseline and Post-treatment Visit. This rate of compensation is commensurate with other AUD research being conducted at the VAPAHCS and the payment mechanism is used by other alcohol/substance abuse research currently conducted at the VA Palo Alto. The total amount of payment is proportional to the participant's time and effort and is intended to facilitate participation without adding undue influence.

l) Costs. Please explain any costs that will be charged to the participant.

No costs will be incurred by any participant.

m) Estimate the probable duration of the entire study. Also estimate the total time per participant for: (i) screening of participant; (ii) active participation in study; (iii) analysis of participant data.

(i) Probable duration of study = 7 years. End date is 30 September 24. Participant recruitment will likely end 30 September 23. Final fiscal year 2024 will be devoted to data processing and analyses.

(ii) Total time per participant:

Study Phase	Estimated Participation Time
Screening:	20-30 min
Baseline:	6.5 hours, 2-4 hours/day over 1 week.
Treatment:	6.5 hours, 40 min/day, over 2 weeks
Follow-up:	Week 5, 4 hours typically over 2 days

Title : Transcranial Magnetic Stimulation for the Treatment of Veterans With Alcohol Use Disorders
Approval Period: 02/28/2025 - 02/28/2026

Follow-up Weeks 9 – 61: 4 hours

Total Active Participation Time = approx. 22 hours over 1 year.

All procedures will be conducted before or after normal ATS clinic hours, or during lunch break, to not interfere with the patient's treatment schedule. The project will be conducted at the VAPAHCS MIRECC Palo Alto Division, which is on the same campus as the FOR program.

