All data including signed consent form documents must be retained for a minimum of three years past the completion of the research. Additional requirements may be imposed by your funding agency, your department, or other entities. (Policy on Retention of and Access to Research Data, Research Policy Handbook, <http://doeresearch.stanford.edu/policies/research-policy-handbook/conduct-research/retention-and-access-research-data>)

APPROVAL LETTER/NOTICE NOTE: List all items (verbatim) that you want to be included in your approval letter (e.g., Amendment date, Investigator's Brochure version, consent form(s) version(s), advertisement name, etc.) in the box below.

Y By checking this box, I verify that I, as the Protocol Director (PD) responsible for this research protocol, have read and agree to abide by the above obligations, or that I have been delegated authority by the PD to certify that the PD has read and agrees to abide by the above obligations.

Data Analyses

Primary Hypothesis:

1a) Veterans who receive active rTMS treatment for AUD demonstrate a significantly lower frequency of relapse at 6 months following treatment than controls (i.e., Veterans with AUD who receive sham rTMS).

Statistical Approach: Primary Hypothesis 1a will be tested with binary logistic regression. The criterion/dependent measure is relapse status (abstained or relapsed during the 6 months after last rTMS session). Treatment group (active rTMS vs. control) is the target predictor, and covariates will include age and composite neurocognitive functioning (based on demographically adjusted RBANS total score) as these variables may account for both within and between subject group variance [89, 91]. PTSD severity (based on PCL-5 total score), substance use severity (based on NIDA Drug Survey composite score), depression severity (based on BDI total score), and/or smoking severity (based on pack-years) will be considered as covariates if, after random assignment, there are post-hoc differences between treatment groups on these variables following breaking of the blind.

1b) Veterans who receive active rTMS treatment for AUD will demonstrate a significantly greater duration of abstinence in the 6 months following treatment than controls.

Statistical Approach: Primary Hypothesis 1b will be tested with Cox regression. The criterion/dependent measure is duration of abstinence after final rTMS session, and covariates include those listed for Primary Hypothesis 1a.

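### Both primary outcomes need an unbroken 6-month drinking history, but each monthly contact looks back only 30 days, and the plan gives no way to recover or score a month whose contact was missed or materially late

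*Combined protocol and SAP*

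**What the plan says.** Section 2a (Protocol Summary item 6, and Monthly Follow-ups) states that for one year after treatment "participants will be contacted monthly, via telephone or in person", to complete short measures of alcohol use, substance use and "craving to assess for changes in these variables over the preceding 30 days". The same paragraph says that "tracking sobriety is the primary outcome measure of this study", so these contacts are the source of the primary outcome.

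The Data Analyses section sets two primary outcomes. For hypothesis 1a, the dependent variable in a logistic regression is "relapse status (abstained or relapsed during the 6 months after last rTMS session"). For hypothesis 1b, analysed by Cox regression, "The criterion/dependent measure is duration of abstinence after final rTMS session".

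Section 8m lists a follow-up visit at "Week 5, 4 hours typically over 2 days" and then "Follow-up Weeks 9 – 61: 4 hours". It does not state the spacing of the later contacts or any window around them. Section 8k offers an extra payment only if every monthly contact from week 9 to week 25 is completed, so missed contacts are foreseen. Breath and urine tests are described at baseline, during treatment and after treatment (Sections 2a and 9c), but not at the monthly contacts.

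**The concern.** A fixed 30-day look-back gives a continuous history only if every contact takes place close to its due date. Suppose a participant misses month 3, drinks that month, and truthfully reports 30 clean days at month 4. The stated look-back has been followed, yet no record of the relapse exists. If the drinking continues, month 4 detects it, but its start is dated no earlier than the first day of the month-4 window.

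The first case affects 1a and the second affects 1b. Neither looks like dropout, because the participant is back in contact and appears fully observed, so a rule for participants lost to follow-up would not catch it. Drinking may also be a reason for missing a call, in which case gaps would tend to fall where the events are. If missed contacts differ between arms, the comparison is biased as well as blurred. With 50 participants per arm, a few misclassified participants matter.

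**Working it through.** The plan gives no missed-contact rate, alpha, power or effect size, so there is no planned figure to reproduce. The steps below measure the gap and then illustrate its effect.

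**1. Length of the gap.** Inputs: a 30-day look-back (Section 2a); a 6-month window of 365.25/2 = 182.6 days; spacing not stated, so taken as 28 days or as a calendar month (30.44 days). After k consecutive missed contacts, unobserved days = (k + 1) × spacing − 30.

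| Situation | 28-day spacing | Calendar month |
|---|---|---|
| All on time | none (2 days' overlap) | 0.4 day per interval |
| One contact missed | 2 × 28 − 30 = 26 days (14.2%) | 2 × 30.44 − 30 = 30.9 days (16.9%) |
| Two in a row missed | 54 days (29.6%) | 61.3 days (33.6%) |
| One contact 7 days late | 5 days | 7.4 days |
| One contact 14 days late | 12 days | 14.4 days |

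**2. How many participants are affected.** With a chance m of missing each of six contacts independently (assumed), the share missing at least one is 1 − (1 − m)^6. This gives 26%, 47% and 74% for m = 5%, 10% and 20%.

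**3. Effect on relapsers.** Assumptions: six 30-day windows; constant hazard with 60% relapsed by day 180 (the 6-month figure in Section 1b, used as a proxy); contacts missed at random with probability m; a share c of relapses confined to one month, the rest continuing. Only relapsers who attend the 6-month contact are counted, so the gap must fall in months 1 to 5. The share of relapses in those months is w = (1 − 0.4^(150/180))/0.6 = 0.89.

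- No recorded relapse: c × m × w.
- Recorded late: (1 − c) × m × w.

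For m = 20% and c = 30%:

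- No recorded relapse: 0.30 × 0.20 × 0.89 = 5.3%.
- Recorded late: 0.70 × 0.20 × 0.89 = 12.5% (12.4% by simulation).
- Mean delay: about 15 days to the end of the missed month plus about 6 days for further consecutive misses, or about 21 days.

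Over m = 10% to 40% and c = 10% to 50%, the share with no recorded relapse runs from 0.10 × 0.10 × 0.89 = 0.9% to 0.50 × 0.40 × 0.89 = 17.8%. At the upper end, observed relapse falls from 60% to 60% × (1 − 0.178) = 49%.

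**4. How much the unstated scoring rule matters.** Take true relapse of 60% on sham and 40% on active (the latter assumed), 50 per arm, and a two-sided 0.05 test of two proportions (assumed). Power with complete data is 0.52. Now let 20% of contacts be missed.

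- Gaps scored as abstinence, a quarter of relapses confined to one month: 60% × (1 − 0.20 × 0.25) = 57% against 40% × 0.95 = 38%; power 0.48.
- Any missed contact scored as relapse: 1 − 0.4 × 0.8^6 = 90% against 1 − 0.6 × 0.8^6 = 84%; power 0.12.

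**5. Unequal missed contacts.** With no true effect (60% in both arms), gaps scored as abstinence, and contacts missed in 10% (sham) against 20% to 30% (active), the spurious difference is 60% × c × (difference in m). For c between 25% and 100% this runs from 0.60 × 0.25 × 0.10 = 1.5 points to 0.60 × 1.00 × 0.20 = 12 points.

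**The case against.** The strongest reply is that the documents do not fix what happens to an uncovered month. A reader might infer that it is scored as abstinence, but no passage says so; it could equally be scored as relapse, as missing or as censored. A reader might also infer that drinking in that month is never asked about. That is too strong: Section 2a is a summary, the interview forms are listed as attachments but not shown, and Section 9c foresees participants disclosing a relapse during follow-up without limiting this to 30 days. Both points stand. What remains is that the only documented look-back is 30 days and that no recovery or scoring rule is written.

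A further inference would be that days go unobserved even when no call is missed, because the post-treatment assessment falls early: "Within 3-4 days of completion of the Treatment Phase, all participants will repeat neurocognitive assessment". That depends on the day from which weeks are counted, and it disappears if the visit is at week 5 and the next contact at week 9, as Section 8m lists. It is not part of this point. Nor does slight lateness matter: at 28-day spacing, a contact up to 2 days late loses nothing.

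It is also fair that the sizes rest on assumed rates, and that the 60% in Section 1b refers to a major relapse period, which may be less likely than a single drink to fit inside one missed month. In the central case, 5% of about 30 relapsers per arm is one or two people.

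Finally, the planned dates (recruitment ending in 2023, study end in September 2024) suggest that follow-up may be complete under the 2025–2026 approval. That limits the change to the interview, but not the change to the analysis.

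**Conclusion.** The point holds as a mismatch between what the primary outcomes require and what the documented contacts collect, with no written rule for bridging it. The gap length follows from the stated 30-day look-back and the two plausible spacings: about 26 to 31 days, or 14% to 17% of the window, for each isolated missed contact. A relapse confined to the gap can go unrecorded in 1a; a continuing one is still found for 1a but can be dated up to about a month late in 1b after one missed contact.

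The effect on results is illustrative only: about 5% of relapsers unrecorded and about 12% dated late in the central case, with about 1% to 18% unrecorded over the ranges tried. It depends on the assumed missed-contact rate, the assumed share of single-month relapses, a constant hazard and the borrowed 60%. The documents do not support saying that the plan scores uncovered months as abstinent. Because they state no rule, the choice could be made after the data are seen, and step 4 shows that it can move the observed rates considerably. The change should be made; it affects how the primary comparison can be interpreted.

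**What to change.** **Data collection, for any contacts still to come.** For alcohol use, replace the 30-day look-back with *since the last completed contact (or since the last TMS session at the first contact)*, and record dates of drinking. Keep the 30-day scale scores unchanged.

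**Analysis, for intervals already uncovered.** Write the following into the Data Analyses section before unblinding, or label it post hoc if the blind is already broken:

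- In 1b, treat the relapse date as interval-censored between the last covered abstinent day and the first positive report.
- In 1a, do not count an uncovered interval as abstinent by default. State how a participant with a gap and no positive report enters the model, for example with relapse status treated as missing.
- Add sensitivity analyses that score uncovered intervals as relapse and as abstinence, and report missed contacts by arm.

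**Separately,** reconcile the post-treatment visit timing in Section 2a (3–4 days after treatment) with week 5 in Section 8m.

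The cost is one changed interview question, a few more minutes after a missed call, and a little more analysis work. The drawback is somewhat poorer recall over windows longer than 30 days. If follow-up is already complete, only the analysis changes apply.
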